#### **Adverse events of special interest (AESI)**

The summaries on the following AESI will be produced by SOC and PT.

Events of interest	Standard MedDRA Query Category plus additional High Level Terms or Preferred Term, if applicable
Anticholinergic events	Anticholinergic syndrome (narrow and broad search SMQ) Glaucoma (narrow search SMQ) Additional PTs: sinus tachycardia, supraventricular tachycardia, ventricular tachycardia, heart rate increased, palpitations, pupillary reflex impaired, pupils unequal, visual disturbance, constipation, gastrointestinal obstruction, ileus paralytic, urinary tract infection, cystitis, urinary incontinence, incontinence, dysuria, urge incontinence, urine flow decreased, bladder irritation, oropharyngeal pain, dysphonia, laryngitis, pharyngitis, and throat irritation
Pneumonia	All PTs that contain the term pneumonia

#### **4.2.5.4 Clinical laboratory variables**

There will be no report of the laboratory data.

Patients who meet the potential Hy’s Law criteria from the first dose of double-blind IP to within 15 days after the last dose of double-blind IP will be summarized. A supportive listing will be provided. Related data collected in the eCRF (e.g., abnormal liver biochemistry risk factors, liver disease signs and symptoms, liver diagnostic tests) will be listed.

#### **4.2.5.5 Vital signs**

Descriptive statistics for vital signs (pulse rate, systolic and diastolic BP, and weight) and changes from baseline values at each visit and at the end of study will be presented.

The number and percentage of patients with PCS postbaseline values will be tabulated. The percentages will be calculated relative to the number of patients with available baseline values and at least one postbaseline assessment in the treatment period. The numerator will be the total number of patients with available baseline values and at least one PCS postbaseline value in the treatment period. A supportive tabular display of patients with PCS postbaseline values

will be provided, including the PID number and baseline and all postbaseline (including non-PCS) values. A tabular display of all AEs occurring in patients who have PCS postbaseline vital sign values will also be provided.

#### **4.2.5.6 Electrocardiogram**

Descriptive statistics for ECG parameters (i.e., ventricular heart rate, RR interval, PR interval, QRS duration, QT interval, QTcB, and QTcF) and changes from baseline values at each assessment time point to the end of study will be presented.

The number and percentage of patients with PCS postbaseline ECG values will be tabulated. The percentages will be calculated relative to the number of patients with available baseline values and at least one postbaseline assessment in the treatment period. The numerator will be the total number of patients with available baseline values and at least one PCS postbaseline value in the treatment period. A supportive tabular display of patients with PCS postbaseline values will be provided, including the PID number, baseline, all postbaseline (including non-PCS) values, and change from baseline. In addition, a tabular display showing all AEs that occurred in patients who had postbaseline PCS ECG values will be provided.

A shift table from baseline to the end of study in the Investigator's overall interpretation of the ECG will be presented for the following categories: normal; abnormal, not clinically significant (NCS); and abnormal, clinically significant (CS).

Shift tables for ECG abnormal findings will be presented overall (in subjects with normal baselines and all subjects in FAS) and by visit.

#### **4.2.5.7 Physical examination**

A listing of physical examination findings at Screening (Visit 1A) will be provided as a part of the medical and surgical history listing. Any new physical examination finding or change (worsening) since the previous physical examination during the treatment period will be provided as part of the AE listing.

#### **4.2.5.8 All-cause mortality**

All-cause mortality based on patient's vital status data will be analyzed using the same method as the primary safety endpoint using a 95% CI and without statistical testing for NI (NI margin will not be used).

### **4.2.6 Health economics and outcomes research analyses**

#### **4.2.6.1 COPD assessment tests (CAT) by visit**

Descriptive statistics will be provided at baseline (actual scores) and each postbaseline visit (actual and change from baseline scores).

Change from baseline in CAT total score by visit will be compared between aclidinium group and placebo using a MMRM model on patients with a baseline CAT total score and at least

one post-randomization CAT total score in the FAS Population. The dependent variable will be the change from baseline in CAT total score at postbaseline protocol-specified visits (up to Visit 12 or EOT visit). Treatment group will be fitted as the explanatory variable, and baseline CAT total score as covariate, and baseline ICS use, smoking status, visit, and treatment group-by-visit interaction as fixed effect factors. Visit will be fitted as a categorical variable, and the variance-covariance matrix will be assumed to be unstructured. Kenward Roger approximation will be used to estimate denominator degrees of freedom. If the procedure does not converge then a compound symmetric variance-covariance matrix will be used instead. The model is as follows:

*Change in CAT total score = treatment group + baseline CAT total score + baseline ICS use + smoking status + visit + treatment\*visit*

Each treatment effect and treatment difference between aclidinium and placebo at each visit will be estimated by their LS means and the differences in LS means on the treatment-by-visit interaction, along with their SEs, and 95% CIs and the p-value corresponding to the between-treatment-group difference. In addition, the overall treatment effect and treatment difference over the treatment period will be estimated by the LS means and the difference in LS means on the treatment factor, along with the SEs, and 95% CIs and the p-value corresponding to the between treatment group difference.

A longitudinal plot will be used to display the change from baseline in CAT total score at each visit by treatment group.

Change from baseline in CAT total score by visit will be analyzed for the following 2 subgroups:

- LABA users (with and without ICS)
- LABA/ICS users

That is, data for each subgroup will be extracted first, then do analysis on each set of data using the same approach as the primary analysis.

In addition, the number (%) of patients experiencing response (improvement of 2 or more units from baseline in CAT total score) will be presented by visit. The number of patients who experience response will be analyzed based on a logistic random effect model with baseline CAT total score as covariate, and treatment group, baseline ICS use, smoking status, visit and treatment group-by-visit interaction as fixed effects and a random intercept to account for the variability between subjects. The estimated treatment effect (i.e., the odds ratio of aclidinium over placebo), corresponding 95% CI, and two-sided p-value for the odds ratio will be presented. The model is as follows:

*Response (Yes=1/No=0) = treatment group + baseline CAT total score + baseline ICS use + smoking status + visit + treatment\*visit*

## **5. CHANGES OF ANALYSIS FROM PROTOCOL**

The primary efficacy endpoint, rate of moderate or severe COPD exacerbations per patient per year during the first year of treatment, will be analyzed using on-treatment analysis as primary analysis and on-study analysis as secondary analysis (per the CSP, on-treatment analysis as primary analysis and on-study analysis as sensitivity analysis).

The covariates or factors included in the models are harmonized.

The incidence of common (e.g.  $\geq 2\%$  of patients in any treatment group) TEAEs will be summarized by preferred term (per the CSP, by SOC and PT).

Number (%) of patients with any SAEs is summarized by SOC, HLT, and PT (per the CSP, by PT).

Number (%) of patients with adverse events with outcome of death is summarized by SOC and PT (per the CSP, by PT).

Number (%) of patients with AEs leading to premature discontinuation of the IP is summarized by SOC and PT (per the CSP, by PT).

The denominator and numerator for PCS vital sign and ECG values are re-defined.

## **7. APPENDIX**

The changes in the appendices only will not need a SAP amendment, instead the revised appendix will be considered as an addendum of the SAP.

## Appendix 1: Imputation of unobserved exacerbations

Assume a patient has  $y_1$  exacerbations during period 1 and then withdraws. We want to estimate  $y_2$ , the number of unobserved exacerbations, given what we have actually seen. Numbers of events before and after withdrawal are seen as two periods with a joint negative multinomial distribution, with  $Y_1$  observed and  $Y_2$  unobserved. For a given patient, distribution  $Y_2|Y_1$  is a function of:

- Observed  $y_1$
- Estimated dispersion (assumed same in both periods)
- Estimated mean (model predicted) rate period 1
- Imputed mean rate period 2 – options for this depends on the method: missing at random (MAR), CR, J2R chosen)

In the CR approach, a patient's expected event rate both before and after withdrawal is assumed to be the same as the reference group. This mimics the case where those withdrawing are in effect nonresponders. When a patient on test treatment has more events before withdrawal than expected for them if they had been in the reference arm, then this 'positive residual' will feed through into a higher than expected event rate in the postwithdrawal period. This is because their earlier observed higher than normal event rate suggests a personal high propensity to events. Postwithdrawal data in the reference arm are imputed under randomized arm MAR.

In the J2R approach, dropouts on test treatment are assumed to have been on test treatment rather than the reference prior to dropout. In the FDA's opinion, this may be more reasonable than the CR approach, given that the CR approach may carry forward a treatment effect (i.e., if a patient had a decreased rate while on treatment). The CR approach is likely inappropriate since effects of bronchodilators are expected to diminish within a few weeks of discontinuation and because such patients will not benefit from the drug in the long-term.

Whichever imputation model is chosen, the subsequent procedure follows that of standard MI. For each imputation, a single set of data is created for each subject's missing data conditional upon their observed data. After summing observed and imputed values for each subject, each imputed data set is analyzed using the model used for the primary analysis. At least 1000 imputations are recommended and more should be considered, to provide sufficiently stable and reproducible results.

Multiple imputation:

- Take a random sample from  $Y_2|Y_1$ , add this to the  $y_1$  we observed for the patient
- Analyse the data using PROC GENMOD as usual
- Repeat analysis multiple times
- Combine estimates using Rubin's rules

### Implementation in SAS:

This approach to sensitivity analysis as described above can be implemented in the SAS system using the GENMOD procedure to derive and sample from the posterior distribution for  $k$ ,  $\beta$  and the other covariate regression parameters. A sample can be drawn from the conditional distribution for the unobserved period using a DATA step. Results can be summarized using the MIANALYZE procedure, which applies Rubin's formula.

The following SAS code extracts samples from the posterior distribution of model parameters including the dispersion parameter using a Bayesian negative binomial log-link model with an offset variable which holds the log of the exposure time for each patient:

Specifically for the sensitivity analysis using copy reference approach on the primary analysis of the primary efficacy endpoint in this study, using only the data from the placebo, run genmod using the primary analysis model (including all the covariates and offset) without treatment, and using Bayes statement with "coeffprior = normal", output a posterior sample of the model parameters of size N. The rationale of using only the placebo's group data is that when we explore the effect of the missing values we assume the missing values are treatment related. Therefore, when estimate the model parameters we do not want the missing values from the active group to contaminate the estimates.

For each draw (after thinning) the expected number of events is calculated for the period before and after withdrawal for each subject. This depends upon the length of time before and after withdrawal. Denote these as  $y1\_hat$  and  $y2\_hat$ .

The design matrices for an individual patient are modified to assign the withdrawing patient to the desired treatment arm for the observed or unobserved period (depending on the method: MAR, CR, J2R chosen).

Then according to the derivation for the conditional distribution  $Y2|Y1$ , we can sample using the following statement:

where  $invK\_hat$  is the inverse of the sampled dispersion parameter, and  $y1$  is the actual count before withdrawal.

The entire number of exacerbations (observed and unobserved) is then:

CCI

CCI

These imputed numbers are then analyzed in a new series of further GENMOD runs (one for each draw), using the standard model (same covariates etc.) and a negative binomial model. However an offset will usually now not be required as the effective period at risk is the same for every patient. Derived parameters from the model such as least squares means for treatment and their differences are then combined across imputation data sets using Rubin's formula, as implemented in the MIANALYZE procedure. These and their confidence interval limits are then exponentiated to derive relative rates.

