## 1.2 Study design

This is a Phase IV, multicenter, randomized, double-blind, placebo-controlled, parallel-group study evaluating the effect of Acclidinium Bromide (a long-acting muscarinic antagonist delivered by the Pressair® dry powder inhalation [DPI] device) compared with placebo on long-term CV safety and COPD exacerbations in outpatients at least 40 years of age who have been diagnosed with moderate to very severe COPD (postbronchodilator % predicted forced expiratory volume in 1 second [FEV1] < 80% and FEV1/forced vital capacity [FVC] ratio < 70%) and a history of CV or cerebrovascular disease and/or significant CV risk factors.

Note: in this document

1. The term “double-blind treatment period” applies to the following 2 scenarios:
  - When used in “maximum of 36-months double-blind treatment period”
  - When used for patients who completed 36-months treatment (completer)
2. The term “during the treatment period” refers to on-treatment period.
3. The term “during the whole study period” refers to both on-treatment and off-treatment (post-treatment follow-up) periods.

The study consists of two-week washout/run-in period (for patients on a long-acting muscarinic antagonist [LAMA]) followed by a maximum of 36-month double-blind treatment period.

Signed informed consent form (ICF) from the patient or the patient’s legally authorized representative will be obtained before any study-related procedures are begun. All patients will be assigned a patient identification (PID) number via the interactive web response system (IWRS). Patients meeting the entry criteria for this study will be randomized (1:1) to acclidinium bromide 400 µg (abbreviated as acclidinium hereafter) twice a day (BID) or placebo BID. This study will conclude when 122 patients have experienced an adjudicated MACE.

Patients who prematurely discontinue investigational product (IP) will participate in a post-treatment follow-up period. The follow-up period will include on-site visits and telephone visits to collect MACE, COPD exacerbations, concomitant medications, and SAEs for the remainder of the study duration.

An independent Data Safety Monitoring Board (DSMB) will be established for this study. The DSMB will periodically monitor and review relevant clinical safety data, including adjudicated MACE.

Patients will be assessed according to the Schedule of Evaluations (See Section 2 of the clinical study protocol [CSP]).

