## **3. PRIMARY AND SECONDARY VARIABLES**

### **3.1 General principles taken for analysis variables**

#### **3.1.1 End of study date**

The study will be completed when a total of 122 patients with adjudicated MACE are observed. Based on the number of adjudicated MACE events, the sponsor will declare the end of the study date and give the study sites at least 3 months notice. At the conclusion of the treatment period, the following information will be collected for all patients (these visit procedures also apply for a patient who is discontinuing study medication before the end of the study):

- All assessments listed for the EOT visit
- Schedule a phone contact for 15 days from visit

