## 4.2 Analysis methods

### 4.2.1 Patient disposition

A clear accounting of the disposition of all patients who enter the study will be provided, from screening to study completion. Summaries of patient disposition will be presented by treatment and overall (column), while summaries in the Screened Population (when applicable) will be presented only by overall (column). The following patient disposition summaries will be provided:

- Number and percentage of patients in the Screened, Randomized, and FAS populations by country and overall (row) (Analysis Population: Screened).
- Number and percentage of screen-failure patients (i.e., patients screened but not randomized), further classified by reasons for screen failure (Analysis Population: Screened).

- Number and percentage of patients who complete the double-blind treatment period and who prematurely discontinue from the double-blind IP, further classified by reasons for premature discontinuation from the double-blind IP (as recorded on Subject Status [IP Usage] page of the eCRFs); number and percentage of patients who prematurely discontinue from the double-blind IP and entered into post-treatment follow-up period and who prematurely discontinued from the double-blind IP and did not enter into post-treatment follow-up period will also be summarized (Analysis Population: FAS).
- Number and percentage of patients who complete the study and who withdraw from the study, further classified by reasons for withdrawal from the study (as recorded on Termination/Death page of eCRFs). Patients who complete the study are those who by the time the study is stopped 1) complete the 36-months double-blind treatment period, 2) prematurely discontinue the double-blind IP and complete the PTFU period, 3) are on treatment, or 4) prematurely discontinue the double-blind IP and are in the PTFU period. Number and percentage of patients who prematurely discontinued treatment, entered into PTFU, but prematurely discontinued the PTFU will also be summarized (Analysis Population: FAS).

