- Number and percentage of patients who complete the first year of treatment and who prematurely discontinue from the double-blind IP during the first year, further classified by reasons for premature discontinuation from the double-blind IP during the first year (as recorded on Subject Status [IP Usage] page of eCRFs); number and percentage of patients who prematurely discontinued from the double-blind IP during the first year and entered into post-treatment follow-up period and who prematurely discontinued from the double-blind IP during the first year and did not enter into post-treatment follow-up period will also be summarized (Analysis Population: FAS).
- Number and percentage of patients characterized at the key time point (e.g., one year) who remained on treatment through that time point, discontinued treatment but remained in study through that time point, withdrew from the study prior to that time point, or did not reach that time point due to study closure (Analysis Population: FAS).
- Time (in days) to premature discontinuation from the double-blind IP based on Kaplan-Meier (KM) method and displayed graphically using KM curves. A log-rank test (two-sided) will be used to compare time to premature discontinuation from the double-blind IP between the two treatment groups (Analysis Population: FAS). Patients who did not discontinue from the double-blind IP will be censored at their last dose of IP.
- Time (in days) to withdrawal from the study will be analyzed using the same methods as described above for analysing time to premature discontinuation from the double-blind IP (Analysis Population: FAS). Patients who did not discontinue from the study will be censored at their last visit date on the study.
- A plot of time to discontinuation from the double-blind IP versus reasons for discontinuation from the double-blind IP will be presented to illustrate patterns of

missing data, with different symbols for treatment groups (Patients who discontinued from the double-blind IP).

The following by-patients listings will be provided:

- Patients who prematurely discontinued the double-blind IP during the first year of treatment will be listed, including, but not limited to, reason for premature discontinuation from the double-blind IP, exposure (days), day of last visit, and status of entering into post-treatment follow-up period (Analysis Population: FAS). Where  

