#### 4.2.4.1 Primary efficacy outcome variable

The primary efficacy variable is rate of moderate or severe COPD exacerbation per patient per year during the first year of treatment. The primary analysis (on-treatment analysis) is to compare rate of moderate or severe COPD exacerbation per patient per year during the first year of treatment between aclidinium and placebo in patients in the FAS. Patients will be analyzed according to randomized treatment.

The null hypothesis is that the exacerbation rate on aclidinium is equal to the exacerbation rate on placebo. The alternative hypothesis is that the exacerbation rate on aclidinium is not equal to the exacerbation rate on placebo, i.e.:

$$H_0: \text{Rate ratio (aclidinium over Placebo)} = 1$$

versus

$$H_a: \text{Rate ratio (aclidinium over Placebo)} \neq 1$$

Exacerbation rate in aclidinium group will be compared to exacerbation rate in the placebo group using a negative binomial regression model. The response variable in the model will be the number of moderate or severe COPD exacerbations experienced by a patient during the first year of treatment. The model will include treatment group, baseline ICS use, baseline COPD severity, history of at least one exacerbation in the past year, and smoking status as factors. In order to adjust for the exposure for each patient, the natural logarithm of the exposure time (in years) during the first year of treatment will be used as an offset variable. When used as the offset variable, the exposure time will be adjusted by subtracting the time when a patient experienced COPD exacerbation(s) (i.e., not at risk during an exacerbation). The model is as follows:

*Number of moderate or severe exacerbations during the first year of treatment = treatment group + baseline ICS use + baseline COPD severity + history of at least one exacerbation in the past year + smoking status*

The estimated treatment effect (i.e., the rate ratio of aclidinium over placebo), corresponding 95% CI, and two-sided p-value for the rate ratio will be presented. In addition, the exacerbation rate and the corresponding 95% CI within each treatment group will be presented.

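### SAP Appendix 1 treats the exposure offset as usually unnecessary because all patients have the same period at risk, but event-driven closure can leave late-randomized patients with less than a year

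*SAP*

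**What the plan says.** Appendix 1 imputes exacerbation counts for a patient who withdraws. It adds them to the observed count and refits the negative binomial model to each completed data set. On the offset in those refits it says: "However an offset will usually now not be required as the effective period at risk is the same for every patient".

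Other sections of the SAP bear on whether the periods are equal:

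- **Section 1.2:** "This study will conclude when 122 patients have experienced an adjudicated MACE". The 36-month treatment period is a maximum.
- **Section 3.1.1:** once the event count is reached, "the sponsor will declare the end of the study date and give the study sites at least 3 months notice". The SAP states no minimum follow-up per patient.
- **Section 4.2.1, key time point (one year is the example):** the disposition table has a separate category for patients who "did not reach that time point due to study closure", distinct from those who stopped treatment or left the study.
- **Section 4.2.1, completion:** "Patients who complete the study are those who by the time the study is stopped" include patients still on treatment at that moment. They are completers, not withdrawals.
- **Section 4.2.4.1:** the primary model uses the log of first-year exposure, less time spent in exacerbation, as its offset.

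**The concern.** The reason given for leaving out the offset is that every patient has the same time at risk once missing counts are filled in. A patient randomized late and closed out at, say, eight months while on drug has not withdrawn, so the withdrawal imputation does not clearly apply. Nothing in the visible text says how that patient enters the J2R or CR analysis.

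Two implementations are possible:

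- **Reading A (closer to the text):** impute withdrawals only and fit without an offset. The eight-month count is then analysed as a twelve-month count.
- **Reading B:** fill everyone to one year so that the premise becomes true. Closed-out aclidinium patients then receive the reference rate although they never stopped drug.

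J2R and CR are named robustness checks on the primary efficacy result. Reading A distorts the rates and the dispersion. Reading B dilutes the ratio for a reason unrelated to dropout. Two programmers could produce different results from the same text.

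Separately, because the primary model subtracts exacerbation time, time at risk is not strictly equal even among patients followed for a full year.

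**Working it through.** **Inputs from the SAP.** Section 1.3.1: 4,000 patients, 122 events, 1.9 MACE per 100 patient-years, 20% study discontinuation at year 2, exponential times. Section 1.3.2: rate ratio 0.86, placebo rate 0.8 per year, k = 0.67, 30% treatment discontinuation in year 1. Section 1.2: 1:1 allocation, 36-month maximum.

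**Assumption.** Accrual is not given. I take it as uniform over A years and vary A.

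**Step 1. Reproduce the plan's figures.**
- Events: 4 × (1.960 + 1.282)² / (ln 1.8)² = 121.7, so 122.
- Patient-years: 122 / 0.019 = 6,421, against the stated 6,500.
- Efficacy power: the discontinuation hazard is −ln(0.70) = 0.357 per year, so mean first-year exposure is (1 − 0.70)/0.357 = 0.841. SE(log RR) = √{[1/(0.8 × 0.841) + 1/(0.8 × 0.86 × 0.841) + 2 × 0.67]/2000} = 0.0477. Power is 88.5%, against about 89% stated.

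**Step 2. When does the study close?** The study-dropout hazard is −ln(0.80)/2 = 0.112 per year. With follow-up f, the event probability is 0.019/(0.019 + 0.112) × (1 − exp(−0.131 f)). Following all 4,000 patients for 36 months would give about 189 events, so closure at 122 must cut follow-up short for some. Closure time T is where expected events equal 122.

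**Step 3. Who falls short of a year?** The shortest planned follow-up is m = T − A. If m < 1, the share with less than a year is q = (1 − m)/A, and their available time is uniform between m and 1. Mean available first-year time is P = 1 − q(1 − m)/2.

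**Step 4. Reading A (withdrawals imputed, no offset).** The fitted placebo rate is 0.8 × P. Apparent dispersion is (1 + 0.67) × E[p²]/P² − 1, with E[p²] = 1 − q + q(1 + m + m²)/3.

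**Step 5. Reading B (everyone filled to a year at the reference rate).** The J2R ratio is 1 − 0.14 × D, where D is mean first-year time on drug before discontinuation or closure. Without truncation D = 0.841 and the ratio is 0.882.

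| A (years) | T (years) | m | q | P | Reading A: placebo rate | Reading A: k | D | Reading B: J2R ratio |
|---|---|---|---|---|---|---|---|---|
| 1.5 | 2.56 | 1.06 | 0 | 1.000 | 0.800 | 0.67 | 0.841 | 0.882 |
| 2 | 2.82 | 0.82 | 8.8% | 0.992 | 0.794 | 0.67 | 0.836 | 0.883 |
| 2.5 | 3.09 | 0.59 | 16.5% | 0.966 | 0.773 | 0.69 | 0.816 | 0.886 |
| 3 | 3.37 | 0.37 | 21.0% | 0.934 | 0.747 | 0.71 | 0.791 | 0.889 |
| 3.5 | 3.67 | 0.17 | 23.7% | 0.902 | 0.722 | 0.76 | 0.765 | 0.893 |

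**Step 6. The ratio under Reading A.** It is 1 − 0.14 × D/P, which runs from 0.882 (A = 1.5) to 1 − 0.14 × 0.765/0.902 = 0.881 (A = 3.5). Keeping a log-period offset gives the same expected ratio, because both arms are truncated alike. At A = 3.5 the complete-data SE rises from 0.0464 with the offset to 0.0473 without it, about 2%. It rises less for shorter accrual.

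**Step 7. Loss under Reading B.** At A = 3.5, 1 − ln(0.893)/ln(0.882) is about 10% of the log effect. At A = 2 it is under 1%. I computed this for J2R only, not for CR.

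**The case against.** The strongest reply is that the sentence is conditional. It says *usually*, and it ties the omission to equal periods, so an analyst who sees unequal periods may keep the offset. Appendix 1 also refers to the primary analysis model, which has one. This stands to the extent that the offset is not forbidden. But equality is asserted as a fact, and no rule says when to keep the offset.

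A reader might also infer more than the documents support:

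- **That Appendix 1 as written gives placebo rates to patients closed out on drug.** It does not say so. Its imputation is worded for patients who withdraw, and section 4.2.1 counts patients on treatment at closure as completers. Reading B is possible but less literal, and it carries all of the dilution in the ratio. Appendix 1 also names own-arm missing-at-random rates, so the two readings are not the only options, although it does not assign those rates to closed-out patients.
- **That J2R significance could be lost because of this.** No calculation shows it. The shift in the ratio is at most about 0.01.
- **That the trial has no minimum follow-up.** The SAP is silent and the protocol is not at hand. The disposition category shows that the case is foreseen, not that it is common.

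The SAS statements in Appendix 1 are partly redacted and might fix the length of the imputed period. That does not repair the premise, which stands in visible text.

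**Conclusion.** The point holds in limited form. The equal-period premise conflicts with sections 1.2, 3.1.1 and 4.2.1, and the handling of patients closed out before one year is not fixed.

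Under the more literal reading, annual rates are understated by about 1-10% for assumed uniform accrual of 2 to 3.5 years. Dispersion rises from 0.67 to at most about 0.76, and the rate ratio is practically unchanged. Under the less literal reading, the J2R ratio moves from about 0.882 to 0.883-0.893. With accrual of 1.5 years or less, neither effect occurs. All of these sizes rest on the assumed accrual pattern and on the SAP's planning rates.

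Only J2R and CR are affected, plus the tipping-point analysis if it reuses the same imputed-data model. The primary analysis keeps its offset. The effect of the exacerbation-day subtraction cannot be sized, because the SAP gives no durations. This is worth correcting before unblinding, but it does not threaten the main efficacy conclusion.

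**What to change.** Section 7 of the SAP lets appendix changes be issued as an addendum without a full amendment. The addendum should:

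1. Define each patient's first-year period as running from the start used in the primary model to the earlier of one year and the study closure date.
2. Impute only from discontinuation or withdrawal to the end of that period, and never beyond closure. Patients on treatment at closure then receive no imputed events.
3. Replace the statement that an offset is usually not required with a requirement to use the log of that period as the offset in every imputed-data GENMOD run.
4. Use the same period for the unobserved time in Appendix 2.
5. State how exacerbation days are treated. Appendix 1 imputes counts without dates or durations, so subtracting days for observed events alone would make time at risk depend on dropout. Either omit the subtraction in the imputed runs and note the difference from the primary model, or apply one stated rule to observed and imputed events alike.

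The cost is a short addendum and a small program change. If nobody is closed out before one year, the closure rule changes nothing.
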